4.5.2.1 Nivolumab and Ipilimumab (Arm A)

Dose delay criteria apply for all drug-related AEs. Treatment delay is up to 6 weeks for nivolumab and up to 12 weeks for ipilimumab from the last dose are allowable (any dose delays greater than these will require approval from the medical monitor). It is permissible in cases of a dose held due to AE to skip the dose in the cycle in order to bring the patient back on track with the next Cycle visit.

Tumor assessments for all participants should continue as per protocol even if dosing is delayed.

Nivolumab and ipilimumab administration should be delayed for the following:

- Grade 2 non-skin, drug-related AE, with the exception of fatigue
- Grade 2 drug-related creatinine, AST, ALT and/or Total Bilirubin abnormalities
- Grade 3 skin, drug-related AE
- Grade 3 drug-related laboratory abnormality, with the following exceptions:
 - Grade 3 lymphopenia or asymptomatic amylase or lipase does not require dose delay
 - Grade ≥ 3 AST, ALT, Total Bilirubin will require dose discontinuation (see section 4.5.5)
- Any adverse event, laboratory abnormality, or intercurrent illness which, in the judgment of the investigator, warrants delaying the dose of study medication.
- Participants receiving ipilimumab in combination with nivolumab that have drug-related toxicities that meet the criteria for dose delay, should have both drugs (ipilimumab and nivolumab) delayed until retreatment criteria are met. (Exceptions apply to the retreatment criteria after dose delay of ipilimumab and nivolumab for Grade ≤ 3 amylase and lipase

abnormalities that are not associated with symptoms or clinical manifestations of pancreatitis and that are attributed to ipilimumab alone.)

- Participants who require delay of nivolumab should be re-evaluated weekly or more frequently if clinically indicated and resume nivolumab dosing when re-treatment criteria are met.

Rescheduling:

- Nivolumab may be delayed until the next planned ipilimumab dose if the next ipilimumab dose is scheduled within the next 12 days. This will permit periodic ipilimumab dosing to be synchronized with nivolumab dosing.

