4.5.4 Criteria to Resume Dosing

4.5.4.1 Criteria to Resume Nivolumab Dosing (Arm A)

Participants may resume treatment with nivolumab when the drug-related AE(s) resolve(s) to Grade ≤ 1 or baseline, with the following exceptions:

- Participants may resume treatment in the presence of Grade 2 fatigue.

- Participants who have not experienced a Grade 3 drug-related skin AE may resume treatment in the presence of Grade 2 skin toxicity.
- Participants who received systemic corticosteroids for management of any drug-related toxicity must be off corticosteroids or have tapered down to an equivalent dose of prednisone ≤ 10 mg/day.
- For participants with Grade 2 AST, ALT and/or Total Bilirubin Abnormalities, dosing may resume when laboratory values return to baseline and management with corticosteroids, if needed, is complete.
- Drug-related pulmonary toxicity, diarrhea, or colitis must have resolved to baseline before treatment is resumed. Participants with persistent Grade 1 pneumonitis after completion of a steroid taper over at least 1 month may be eligible for retreatment if discussed with and approved by the BMS Medical Monitor.

Participants with drug-related endocrinopathies adequately controlled with only physiologic hormone replacement may resume treatment after consultation with the BMS Medical Monitor (or designee). Adrenal insufficiency requires discontinuation regardless of control with hormone replacement.

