4.5.4.2 Criteria to Resume Ipilimumab Dosing (Arm A)

Participants may resume treatment with nivolumab and ipilimumab when drug-related AE(s) resolve(s) to Grade 1 or baseline value, with the following exceptions:

- Participants may resume treatment in the presence of Grade 2 fatigue.
- Participants who have not experienced a Grade 3 drug-related skin AE may resume treatment in the presence of Grade 2 skin toxicity.
- Participants with baseline Grade 1 AST/ALT or total bilirubin who require dose delays for reasons other than a 2-grade shift in AST/ALT or total bilirubin may resume treatment in the presence of Grade 2 AST/ALT or total bilirubin.
- Participants with combined Grade 2 AST/ALT and total bilirubin values meeting discontinuation parameters ([Section 4.5.5.2](#)) should have treatment permanently discontinued.
- Drug-related pulmonary toxicity, diarrhea, or colitis must have resolved to baseline before treatment is resumed.
- Participants who received systemic corticosteroids for management of any drug-related toxicity must be off corticosteroids or have tapered down to an equivalent dose of prednisone ≤ 10 mg/day.
- Drug-related endocrinopathies adequately controlled with only physiologic hormone replacement may resume treatment after consultation with the BMS Medical Monitor.
- Dose delay of ipilimumab which results in no ipilimumab dosing for > 12 weeks requires ipilimumab discontinuation, with exceptions as noted in [Section 4.5.5.2](#).
- Ipilimumab may not be resumed sooner than 6 weeks (± 3 days) after the prior ipilimumab dose.
- In general, participants who meet criteria to resume ipilimumab will also have met criteria to resume nivolumab, so it should be feasible to synchronize dosing of both drugs when resuming

ipilimumab. In order to facilitate this, the dosing days of nivolumab and ipilimumab may be adjusted within the permitted ± 3 day window, as long as consecutive nivolumab doses are given at least 12 days apart.

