4.5.5.1 Nivolumab Dose Discontinuation (Arm A)

Treatment with nivolumab should be permanently discontinued for any of the following:

- Any Grade 2 drug-related uveitis, eye pain or blurred vision that does not respond to topical therapy and does not improve to Grade 1 severity within the re-treatment period OR requires systemic treatment
- Any Grade 3 non-skin, drug-related AE lasting > 7 days, or recurs with the following exceptions for laboratory abnormalities, diarrhea, colitis, neurologic toxicity, drug-related uveitis, pneumonitis, bronchospasm, hypersensitivity reactions, infusion reactions, and endocrinopathies:
 - Grade 3 drug-related diarrhea, colitis, neurologic toxicity, uveitis, pneumonitis, bronchospasm, myocarditis, hypersensitivity reaction, or infusion reaction of any duration requires discontinuation
 - Grade 3 drug-related endocrinopathies, adequately controlled with only physiologic hormone replacement do not require discontinuation. Adrenal insufficiency requires discontinuation regardless of control with hormone replacement.
 - Grade 3 drug-related laboratory abnormalities do not require treatment discontinuation except:
 - ◆ Grade 3 drug-related thrombocytopenia > 7 days or associated with bleeding requires discontinuation
 - ◆ Any drug-related liver function test (LFT) abnormality that meets the following criteria require discontinuation:
 - Grade ≥ 3 drug-related AST, ALT or Total Bilirubin requires discontinuation*
 - Concurrent AST or ALT > 3 x ULN and total bilirubin > 2x ULN
 - * In most cases of Grade 3 AST or ALT elevation, study treatment will be permanently discontinued. If the investigator determines a possible favorable benefit/risk ratio that warrants continuation of study treatment, a discussion between the investigator and the BMS Medical Monitor/designee must occur.
- Any Grade 4 drug-related adverse event or laboratory abnormality (including but not limited to creatinine, AST, ALT, or Total Bilirubin), except for the following events which do not require discontinuation:
 - Grade 4 neutropenia ≤ 7 days
 - Grade 4 lymphopenia or leukopenia or asymptomatic amylase or lipase

- Isolated Grade 4 electrolyte imbalances/abnormalities that are not associated with clinical sequelae and are corrected with supplementation/appropriate management within 72 hours of their onset

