4.5.5.2 Ipilimumab Dose Discontinuation (Arm A)

Ipilimumab should be permanently discontinued if any of the following criteria are met:

- Any Grade \geq 2 drug-related uveitis or eye pain or blurred vision that does not respond to topical therapy and does not improve to Grade 1 severity within 2 weeks OR requires systemic treatment;
- Any Grade \geq 3 bronchospasm or other hypersensitivity reaction;
- Any other Grade 3 non-skin, drug-related adverse event with the following exceptions for laboratory abnormalities, Grade 3 nausea and vomiting, Grade 3 neutropenia and thrombocytopenia, and symptomatic endocrinopathies which resolved (with or without hormone substitution);

- Any drug-related liver function test (LFT) abnormality that meets the following criteria require discontinuation:
 - AST or ALT > 8x ULN
 - Total bilirubin > 5 x ULN
 - Concurrent AST or ALT > 3 x ULN and total bilirubin > 2 x ULN
- Any Grade 4 drug-related adverse event or laboratory abnormality, except for the following events, which do not require discontinuation:
 - Grade 4 neutropenia ≤ 7 days
 - Grade 4 lymphopenia or leukopenia
 - Isolated Grade 4 amylase or lipase abnormalities which are not associated with symptoms or clinical manifestations of pancreatitis.
 - Isolated Grade 4 electrolyte imbalances/abnormalities that are not associated with clinical sequelae and are corrected with supplementation/appropriate management within 72 hours of their onset
- Any treatment delay resulting in no ipilimumab dosing for > 12 weeks with the following exceptions: Dosing delays to manage drug-related adverse events, such as prolonged steroid tapers, are allowed. Prior to re-initiating treatment in a participant with a dosing delay lasting > 12 weeks, the BMS medical monitor must be consulted. Tumor assessments should continue as per protocol even if dosing is delayed.
- Dosing delays resulting in no ipilimumab dosing for > 12 weeks that occur for non-drug-related reasons may be allowed if approved by the BMS medical monitor. Prior to re-initiating treatment in a participant with a dosing delay lasting > 12 weeks, the BMS medical monitor must be consulted. Tumor assessments should continue as per protocol even if dosing is delayed.
- Any adverse event, laboratory abnormality, or intercurrent illness which, in the judgment of the Investigator, presents a substantial clinical risk to the participant with continued ipilimumab dosing

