APPENDIX 2 MANAGEMENT ALGORITHMS

These general guidelines constitute guidance to the Investigator and may be supplemented by discussions with the Medical Monitor representing the Sponsor. The guidance applies to all immuno-oncology agents and regimens.

A general principle is that differential diagnoses should be diligently evaluated according to standard medical practice. Non-inflammatory etiologies should be considered and appropriately treated.

Corticosteroids are a primary therapy for immuno-oncology drug-related adverse events. The oral equivalent of the recommended IV doses may be considered for ambulatory patients with low-grade toxicity. The lower bioavailability of oral corticosteroids should be taken into account when switching to the equivalent dose of oral corticosteroids.

[figure not shown]
Consultation with a medical or surgical specialist, especially prior to an invasive diagnostic or therapeutic procedure, is recommended.

The frequency and severity of the related adverse events covered by these algorithms will depend on the immuno-oncology agent or regimen being used.

GI Adverse Event Management Algorithm

Rule out non-inflammatory causes. If non-inflammatory cause is identified, treat accordingly and continue I-O therapy. Opiates/narcotics may mask symptoms of perforation. Infliximab should not be used in cases of perforation or sepsis.

[figure not shown]

Patients on IV steroids may be switched to an equivalent dose of oral corticosteroids (e.g. prednisone) at start of tapering or earlier, once sustained clinical improvement is observed. Lower bioavailability of oral corticosteroids should be taken into account when switching to the equivalent dose of oral corticosteroids.

27-Jun-2019

Renal Adverse Event Management Algorithm

Rule out non-inflammatory causes. If non-inflammatory cause, treat accordingly and continue I-O therapy.

[figure not shown]

Patients on IV steroids may be switched to an equivalent dose of oral corticosteroids (e.g. prednisone) at start of tapering or earlier, once sustained clinical improvement is observed. Lower bioavailability of oral corticosteroids should be taken into account when switching to the equivalent dose of oral corticosteroids.

27-Jun-2019

Pulmonary Adverse Event Management Algorithm

Rule out non-inflammatory causes. If non-inflammatory cause, treat accordingly and continue I-O therapy. Evaluate with imaging and pulmonary consultation.

[figure not shown]

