Patients on IV steroids may be switched to an equivalent dose of oral corticosteroids (e.g. prednisone) at start of tapering or earlier, once sustained clinical improvement is observed. Lower bioavailability of oral corticosteroids should be taken into account when switching to the equivalent dose of oral corticosteroids

27-Jun-2019

Hepatic Adverse Event Management Algorithm

Rule out non-inflammatory causes. If non-inflammatory cause, treat accordingly and continue I-O therapy. Consider imaging for obstruction.

[figure not shown]
Patients on IV steroids may be switched to an equivalent dose of oral corticosteroids (e.g. prednisone) at start of tapering or earlier, once sustained clinical improvement is observed. Lower bioavailability of oral corticosteroids should be taken into account when switching to the equivalent dose of oral corticosteroids.

*The recommended starting dose for grade 4 hepatitis is 2 mg/kg/day methylprednisolone IV.

27-Jun-2019

Endocrinopathy Adverse Event Management Algorithm

Rule out non-inflammatory causes. If non-inflammatory cause, treat accordingly and continue I-O therapy. Consider visual field testing, endocrinology consultation, and imaging.

[figure not shown]

Patients on IV steroids may be switched to an equivalent dose of oral corticosteroids (e.g. prednisone) at start of tapering or earlier, once sustained clinical improvement is observed. Lower bioavailability of oral corticosteroids should be taken into account when switching to the equivalent dose of oral corticosteroids.

27-Jun-2019

Skin Adverse Event Management Algorithm

Rule out non-inflammatory causes. If non-inflammatory cause, treat accordingly and continue I-O therapy.

Patients on IV steroids may be switched to an equivalent dose of oral corticosteroids (e.g. prednisone) at start of tapering or earlier, once sustained clinical improvement is observed. Lower bioavailability of oral corticosteroids should be taken into account when switching to the equivalent dose of oral corticosteroids.

[figure not shown]
*Refer to NCI CTCAE v4 for term-specific grading criteria.

^If SJS/TEN is suspected, withhold I-O therapy and refer patient for specialized care for assessment and treatment. If SJS or TEN is diagnosed, permanently discontinue I-O therapy.

27-Jun-2019

Neurological Adverse Event Management Algorithm

[figure not shown]
Rule out non-inflammatory causes. If non-inflammatory cause, treat accordingly and continue I-O therapy.

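### Appendix 2 ends immunotherapy once SJS or TEN is diagnosed, but the Arm A dosing sections would allow a Grade 3 case to be re-dosed, and no text says which governs

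*Protocol*

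**What the plan says.** Protocol Appendix 2, in the footnote to the skin algorithm, tells the investigator to withhold immunotherapy when SJS or TEN is suspected, and then: "If SJS or TEN is diagnosed, permanently discontinue I-O therapy". The sentence sets no grade condition.

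The Arm A dosing sections are written by grade and do not name SJS or TEN:

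- **Delay (4.5.2.1).** The listed reasons for holding both drugs include "Grade 3 skin, drug-related AE".
- **Resume (4.5.4.1).** "Participants may resume treatment with nivolumab when the drug-related AE(s) resolve(s) to Grade" 1 or below, or to baseline, subject to listed exceptions.
- **Resume (4.5.4.2).** "Participants may resume treatment with nivolumab and ipilimumab when drug-related AE(s) resolve(s) to Grade 1 or baseline value", again with listed exceptions.
- **Discontinue nivolumab (4.5.5.1).** The Grade 3 criterion begins: "Any Grade 3 non-skin, drug-related AE lasting > 7 days, or recurs".
- **Discontinue ipilimumab (4.5.5.2).** The corresponding criterion begins: "Any other Grade 3 non-skin, drug-related adverse event".

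On authority, Protocol Section 4.5 says that delay, retreatment and discontinuation follow the criteria in 4.5.2 to 4.5.5. It names neither 4.5.7 nor Appendix 2. Section 4.5.7 introduces the algorithms, Skin among them, as an aid to investigators. Appendix 2 says of itself: "These general guidelines constitute guidance to the Investigator".

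**The concern.** Two parts of one protocol give different endings to the same event. The appendix singles out SJS and TEN as a reason to end treatment. The sections that investigators are told to use for dosing decisions treat a Grade 3 skin event as a reason to delay, with a route back to dosing.

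The main issue is participant safety: whether an Arm A participant is re-exposed could depend on which page the site opened. There is also a smaller reporting effect. SAP Section 7.1.1 classifies adverse events as leading to discontinuation or to delay by the action recorded for the study drug. Two sites handling the same event differently would therefore place it in different safety tables.

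**Working it through.** No arithmetic applies. The check follows one diagnosed, drug-related SJS or TEN event in Arm A through each section, by grade.

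| Grade | Delay (4.5.2.1) | Resume (4.5.4.1, 4.5.4.2) | Discontinue (4.5.5.1, 4.5.5.2) | Appendix 2 footnote | Result |
|---|---|---|---|---|---|
| 4 | not needed | not reached | both drugs stop for any Grade 4 drug-related event; the listed exceptions are laboratory or endocrine | stop permanently | agree |
| 3 | both drugs held | allowed at Grade 1 or baseline | Grade 3 criterion limited to non-skin events, so not met on grade | stop permanently | conflict |
| 2 or lower | no listed skin criterion | not applicable | no listed skin criterion | reach at these grades cannot be confirmed | not relied on |

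The Grade 3 row, step by step:

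1. The event meets the skin criterion in 4.5.2.1, so nivolumab and ipilimumab are both held.
2. The resume sections do name particular toxicities. Drug-related pulmonary toxicity, diarrhea and colitis must return to baseline. SJS and TEN are not among those named.
3. The allowance to resume with Grade 2 skin toxicity is closed to anyone who has had a Grade 3 skin event. Recovery to Grade 1 or baseline is therefore needed, with steroids stopped or tapered to 10 mg/day prednisone equivalent or less.
4. Delay limits also apply: more than 6 weeks for nivolumab or 12 weeks for ipilimumab calls for discontinuation, with exceptions that include prolonged steroid tapers.
5. A case that clears steps 2 to 4 may be re-dosed under the body text. Under the footnote it may not.

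The last row is left out for two reasons. The footnote belongs to a flowchart that could not be seen in the text reviewed, so the box carrying its marker is unknown. Grading is also left to an outside scale ("Refer to NCI CTCAE v4 for term-specific grading criteria"), which the documents do not reproduce.

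For precedence, Sections 3.5, 4.5 and 4.5.7 and Appendix 2 were read together. None says what to do when an algorithm and a dosing criterion differ.

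**The case against.** The strongest reply is that this is an omission from a list and not a contradiction. Resumption is permitted, never required. The 4.5.5 lists do not claim to be exhaustive. Section 3.5 requires stopping when the investigator judges that an adverse event makes continuation contrary to the participant's interest. Sections 4.5.5.1 and 4.5.5.2 allow stopping for substantial clinical risk, and 4.5.2.1 allows a hold for any event. Section 4.5.7 sends the reader to Appendix 2 and names Skin. An investigator who stops for good after diagnosed SJS or TEN breaches nothing.

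All of that stands as far as it goes: no text forces re-dosing, and one course of action satisfies both parts. It does not close the gap. A site that follows 4.5.2 to 4.5.5, as Section 4.5 directs, may re-dose after an event that the appendix says ends treatment. The judgement clauses leave that choice to each site.

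It could also be said that Grade 3 hypersensitivity reactions already require discontinuation under both lists. But no text classes SJS or TEN as hypersensitivity, and the protocol places them under Skin. That adds another possible reading and does not settle the matter.

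A reader might infer more than the documents support:

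- *That the delay, resume and discontinuation sections all exempt skin events below Grade 4.* They do not. Grade 3 skin events are held, and the resume rule is stricter after one. Only the Grade 3 discontinuation criteria leave skin out.
- *That the body text compels continued dosing.* Section 3.5 makes stopping mandatory for the 4.5.5 reasons; nothing makes resumption mandatory.
- *That the footnote is binding at every grade, including suspected Grade 1 or 2 cases.* Appendix 2 describes itself as guidance, and its reach at those grades cannot be established here.

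**Conclusion.** The point holds in a narrow form. For a diagnosed, drug-related SJS or TEN event graded 3, the body text permits re-dosing, the Appendix 2 footnote says to stop for good, and nothing ranks the two. At Grade 4 there is no conflict.

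This rests on two assumptions. One is that such an event can be graded below 4, which the documents neither confirm nor exclude. The other is that the footnote applies at Grade 3, which its wording supports because it sets no grade condition, although the flowchart itself was not visible.

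The size cannot be stated. Arm A is planned at about 930 / 2 = 465 participants, but no incidence of SJS or TEN is given, so 465 should not be read as a count of people affected. The concern is safety and consistent handling between sites. The treatment-group assignment for efficacy is untouched, since SAP Section 6.2 analyses efficacy as randomized. It should be corrected because the event is one that the protocol itself singles out and the correction is small.

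**What to change.** Reconcile Protocol Sections 4.5.2.1, 4.5.4.1, 4.5.4.2, 4.5.5.1 and 4.5.5.2 with the Appendix 2 skin footnote, so that a reader of either part reaches the same instruction for SJS and TEN. State, in Section 4.5 or 4.5.7, which text governs when an algorithm and a dosing criterion differ. Which rule to adopt, and at which grades, is for the clinical team.

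The cost is a few lines of protocol wording, with no new data, procedures or analyses. There is a precedent: the change history in Protocol Appendix 6 records that Revised Protocol 03 added Grade 3 myocarditis to the nivolumab discontinuation criteria in response to safety information.

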APPENDIX 3 RECIST 1.1 GUIDELINES

1 EVALUATION OF LESIONS

At baseline, tumor lesions/lymph nodes will be categorized measurable or non-measurable as follows:

1.1 Measurable

Tumor lesions: Must be accurately measured in at least one dimension (longest diameter in the plane of measurement is to be recorded) with a minimum size of:

1. 10 mm by CT scan (CT scan slice thickness no greater than 5 mm)
2. 10 mm caliper measurement by clinical exam (lesions which cannot be accurately measured with calipers should be recorded as non-measurable)
3. 20 mm by chest x-ray

Malignant lymph nodes: To be considered pathologically enlarged and measurable, a lymph node must be ≥ 15 mm in short axis when assessed by CT scan (CT scan slice thickness recommended to be no greater than 5 mm).

Lymph nodes merit special mention since they are normal anatomical structures which may be visible by imaging even if not involved by tumor. Pathological nodes which are defined as measurable and may be identified as target lesions must meet the criterion of a short axis of ≥ 15 mm by CT scan. Only the short axis of these nodes will contribute to the baseline sum. The short axis of the node is the diameter normally used by radiologists to judge if a node is involved by solid tumor. Nodal size is normally reported as two dimensions in the plane in which the image is obtained (for CT scan this is almost always the axial plane; for MRI the plane of acquisition may be axial, sagittal or coronal). The smaller of these measures is the short axis. For example, an abdominal node which is reported as being 20 mm x 30 mm has a short axis of 20 mm and qualifies as a malignant, measurable node. In this example, 20 mm should be recorded as the node measurement. All other pathological nodes (those with short axis ≥ 10 mm but < 15 mm) should be considered non-target lesions. Nodes that have a short axis < 10 mm are considered non-pathological and should not be recorded or followed.

